#### 5.2.6.2 Cycles 5 and Beyond

Procedures below will be done starting at Cycle 5 and every 3 weeks thereafter, unless otherwise specified. All predose procedures below may be performed  $\leq 4$  days in advance of the actual dosing day, with the exception of the following which must be done on the dosing day:

- a. Vital signs
  - Physical exam and body weight
  - Vital signs; refer to Section 5.6.1
    - For AGS-16C3F Subjects: On the days of study drug administration, vital signs will be taken predose, and approximately 30 minutes after administration of study drug
    - For axitinib Subjects: Vital signs will be taken once at each clinic visit
- ECOG Performance Status; refer to Appendix 12.5
- Hematology, chemistry, CRP, and PT/aPTT; refer to Section 5.6.3

- Thyroid Function Test, every odd cycle (e.g., Cycle 5, Cycle 7, etc.); refer to Section 5.6.3
- uPCR, every odd cycle (e.g., Cycle 5, Cycle 7, etc.); refer to Section 5.6.3
- Complete eye exam for AGS-16C3F subjects only will be done after the Cycle 5 Day 1 dose but before the Cycle 6 Day 1 dose, and as clinically indicated; refer to Section 5.6.5
- Complete ESQ at every scheduled and unscheduled visit; refer to Section 5.6.5.1
- PK and ADA blood samples will be collected for AGS-16C3F subjects only; refer to Table 1 and Table 2
- Disease assessment; refer to Section 5.5

### 5.2.7 Post-treatment Follow-Up Period (Safety Follow-Up visit)

All subjects will be required to have a Safety Follow-Up visit at least 28 days (+ 7 days) after the last dose. Every effort should be made to have this visit occur within the specified timeframe. If this visit cannot be performed within the specified timeframe (e.g., subject initiating new treatment, subject admitted to hospice), this visit should be scheduled as close as possible to the specified timeframe. To ensure subject's wellbeing and safety, a Safety Follow-Up visit performed outside of the window is strongly preferred over no Safety Follow-Up Visit.

Procedures below will be done during the Safety Follow-Up Visit, unless otherwise specified.

- Physical exam and body weight
- Vital signs; refer to Section 5.6.1
- ECG in triplicate (approximately 3-5 minutes in between ECGs). Ensure that the subject is in the same position for every reading; refer to Section 5.6.4
- ECOG Performance Status; refer to Appendix 12.5
- Hematology, chemistry, CRP, Thyroid Function Test, PT/aPTT, and uPCR; refer to Section 5.6.3
- Complete eye exam as clinically indicated; refer to Section 5.6.5
- Complete ESQ; refer to Section 5.6.5.1
- PK and ADA blood samples will be collected for AGS-16C3F subjects only, as specified in Table 1 and Table 2.

## 5.3 Demographics and Baseline Characteristics

### 5.3.1 Demographics

Age at first dose, gender, sex, race, ethnicity, height, and body weight will be collected during the Screening visit for this study.

### 5.3.2 Medical History

Medical history will be recorded for all medical conditions within the past 5 years from the date of randomization. Please use the following list as a minimum guideline for what should be collected and entered into the eDC system.

- Record all cancer diagnoses.
- Record all diseases and/or diagnoses requiring cytotoxic treatment (e.g., including non-oncology treatments such as arthritis treated with methotrexate).
- Record all diseases and/or diagnoses of major organs (e.g., myocardial infarction, hepatitis).
- Record all non-renal cell cancer history.

### 5.3.3 Diagnosis of the Target Disease, Severity, and Duration of Disease

A complete medical history of the target disease will be recorded at Screening. This will include:

- RCC diagnosis (date and method of diagnosis, including dates of diagnostic procedures)
- TNM classification and disease stage at screening
- Metastasis diagnosis date
- Dates and type of previous therapy for RCC
- Other disease specific information as designated in the eCRF

## 5.4 Pharmacokinetics Assessment

The PK data for ADC and MMAF will be analyzed using noncompartmental method. Parameters to be assessed will include concentrations at the end of infusion or maximum observed concentration ( $C_{EOI}$  or  $C_{max}$ ), concentrations at trough ( $C_{trough}$ ), time to maximum observed concentration ( $T_{max}$ ), partial area under the concentration time curve ( $AUC_{\tau}$ ) for Cycle 1 and 4, and either terminal or apparent terminal half-life ( $t_{1/2}$ ) as appropriate. Additionally, clearance (CL) and volume of distribution at steady state ( $V_{ss}$ ) will be included as appropriate. Descriptive statistics will be provided for the PK parameter estimates and subject concentration plots over time may be generated. Additional model-based analyses may be performed and reported separately.

## 5.5 Efficacy Assessment

Response and progression will be evaluated in this study using RECIST v.1.1, refer to Appendix [12.6](#). Investigator's radiographic disease assessment will be used for treatment decisions.

Disease assessments will be performed every 8 weeks ( $\pm 7$  days) counting from C1D1. Bone imaging will be performed every 12 weeks ( $\pm 7$  days) counting from C1D1 (only subjects with bone disease at screening).

Those subjects who discontinued the study for reasons other than objective disease progression by RECIST v.1.1 will continue to have disease assessments every 8 weeks ( $\pm 7$

days) counting from C1D1. This will continue until subject has radiologically confirmed progression, initiates a new therapy, study closure or subject dies.

Scans will be read on site.

CT scan with contrast (chest, abdomen, and pelvis) is the preferred modality for tumor assessment. MRI is acceptable if local standard practice, or CT scans are contraindicated in a subject (e.g., subject is allergic to contrast media). All other RECIST-approved scanning methods such as x-ray are optional. PET-CT scans must use contrast. The modality chosen for the subject must be used throughout the study.

Additional instructions for imaging assessments can be found in the study guide. The assessment will include tumor measurements for target lesions, nontarget lesions, and any new lesions. An overall assessment will be characterized for a given time point evaluation. At the end of study for that subject, the best overall response to the study regimen will be characterized. To ensure comparability, the screening and subsequent assessment of response should be performed using identical techniques. The same individual should assess images for any 1 subject for the duration of the study if possible.

For subjects with known treated stable brain metastases at study entry, it is recommended that repeat imaging also include the brain and the same methods used to detect brain lesions at baseline are to be used to follow the lesions throughout the study.

Per RECIST v1.1, lesions that cannot be accurately measured such as bone lesions and previously radiated lesions should not be selected as measurable lesions.

Confirmation scans for CR or PR should be done at the next scheduled assessment. The site of disease progression as well as target or nontarget lesion should be documented in the eCRF. Additional imaging may be performed at any time to confirm suspected progression of disease.

## **5.5.1 Evaluation of Target Lesions**

### **5.5.1.1 Complete Response (CR)**

CR is defined as disappearance of all target and nontarget lesions. Any pathological lymph nodes (whether target or nontarget) must have reduction in short axis to < 10 mm from baseline measurement.

### **5.5.1.2 Partial Response (PR)**

PR is defined as at least a 30% decrease in the sum of diameters (longest for nonnodal lesions, short axis for nodal lesions) of target lesions taking as reference to the baseline sum of diameters.

### **5.5.1.3 Stable Disease (SD)**

SD is defined as neither sufficient decrease to qualify for PR nor sufficient increase to qualify for progressive disease taking as reference the smallest sum of diameters while on study drug.

#### **5.5.1.4 Progressive Disease (PD)**

PD is defined as at least a 20% increase in the sum of diameters (longest for nonnodal lesions, short axis for nodal lesions) of the target lesions taking as reference the smallest sum on study (this includes the baseline sum if that is the smallest on study). In addition to the relative increase of 20%, the sum must also demonstrate an absolute increase of at least 5 mm. The appearance of 1 or more new lesions is also considered progression.

#### **5.5.2 Evaluation of Nontarget Lesions**

To achieve unequivocal progression on the basis of nontarget lesions, there must be an overall level of substantial worsening in nontarget disease such that, even in presence of SD or PR of target lesions, the overall tumor burden has increased sufficiently to merit discontinuation of therapy. A modest increase in the size of 1 or more nontarget lesions is usually not sufficient to qualify for unequivocal progression.

##### **5.5.2.1 Complete Response (CR)**

For CR of nontarget lesions, subjects must have disappearance of all nontarget lesions and all lymph nodes must be nonpathological in size (< 10 mm short axis).

##### **5.5.2.2 NonCR/NonPD**

NonCR/NonPD of nontarget lesions is defined as persistence of 1 or more nontarget lesions.

##### **5.5.2.3 Progressive Disease (PD)**

PD of nontarget lesions is defined as unequivocal progression of existing nontarget lesions or the appearance of 1 or more new lesions.

#### **5.5.3 Evaluation of Time Point Response**

The overall response status at each time point for subjects with measurable disease at baseline will be reported according to Table 1 in Appendix [12.6](#)

### **5.6 Safety Assessment**

#### **5.6.1 Vital Signs**

Measurements consisting of blood pressure, heart rate, respiration rate, and temperature will be collected throughout this trial. Vital signs will be collected according to the schedule displayed in [Table 1](#)

- For subjects randomized to AGS-16C3F, on the days of study drug administration, vital signs will be taken predose, and approximately 30 minutes after administration of study drug
- For subjects randomized to axitinib, vital signs will be taken once at each clinic visit

#### **5.6.2 Adverse Events**

See Section [5.7](#) for information regarding AE collection and data handling.

### 5.6.2.1 Adverse Events Requiring Treatment Modifications and/or Discontinuation of AGS-16C3F Administration

#### 5.6.2.1.1 Thrombocytopenia

For thrombocytopenia without signs and symptoms of bleeding that the investigator considers clinically significant, the following AGS-16C3F dosing guidelines will be used.

**Table 9 Recommended Guidelines for Thrombocytopenia**

Grade	Description	Action
2	Present, without signs and symptoms of bleeding.	The dose may be administered or held at investigator discretion.
	Persistent (i.e., lasting for $\geq 5$ weeks), without signs and symptoms of bleeding, and without documented bone marrow suppression.	The subject may be considered for a dose reduction to 1.2 mg/kg. Dose reduction must be discussed with and approved in writing by the Medical Monitor.
	Persistent (i.e., lasting for $\geq 5$ weeks), without signs and symptoms of bleeding, and with documented bone marrow suppression.	The subject will be discussed with the Medical Monitor. The possible need for permanent discontinuation will be considered based on clinical benefit of treatment as well as review of overall patient profile (concomitant medication and medical history review, presence or absence of mucosal bleed, other AEs, etc.).
3	Present, without signs and symptoms of bleeding.	The dose will be held until platelet count improves to at least Grade 2 ( $\geq 50 \times 10^9/L$ ).
	Present, without signs and symptoms of bleeding, and has not recovered to at least Grade 2 ( $\geq 50 \times 10^9/L$ ) $\leq 5$ weeks.	The subject will either be permanently discontinued or may be considered for a dose reduction to 1.2 mg/kg. Dose reduction must be discussed with and approved in writing by the Medical Monitor.
4	Present, without signs and symptoms of bleeding, and platelet count is confirmed with a repeat lab performed $\leq 72$ hours.	Subject will be permanently discontinued.
	Present, without signs and symptoms of bleeding, and isolated (i.e., not confirmed with a repeat lab $\leq 72$ hours after first assessment).	Dose will be held until platelet count improves to at least Grade 2 ( $\geq 50 \times 10^9/L$ )
	Present, without signs and symptoms of bleeding, and isolated (i.e., not confirmed with a repeat lab $\leq 72$ hours after first assessment), and has not recovered to at least Grade 2 ( $\geq 50 \times 10^9/L$ ) $\leq 5$ weeks.	The subject will either be permanently discontinued or may be considered for a dose reduction to 1.2 mg/kg. Dose reduction must be discussed with and approved in writing by the Medical Monitor.

Beginning at Cycle 5 Day 1 and for all subsequent cycles, a bone marrow study or hematology consult, is strongly encouraged for all AGS-16C3F subjects whose predose platelet count is  $< 75 \times 10^9/L$  at any 2 timepoints. If a hematology consult and/or bone

marrow study is/are performed, the redacted report(s) will be timely submitted to the Sponsor.

#### 5.6.2.1.2 Adverse Events of Possible Hepatic Origin

See Appendix 12.2 for detailed information on the monitoring and assessment of liver abnormalities, if the AE for a subject enrolled in a study and receiving study drug is accompanied by increases in liver function testing (LFT, e.g.: AST, ALT, bilirubin, etc.) or is suspected to be due to hepatic dysfunction.

Subjects with AEs of hepatic origin accompanied by Liver Function Test (LFT) abnormalities should be carefully monitored.

#### 5.6.2.1.3 Other Adverse Events

Subjects who experience a Grade 4 toxicity other than those related to the eye, liver, and thrombocytopenia, as described in Sections 5.6.5, 5.6.2.1.2, 5.6.2.1.1 will be permanently discontinued from AGS-16C3F treatment. Laboratory AEs with a Grade 4 value, must be confirmed with a repeat analysis  $\leq 72$  hours before discontinuing subject from treatment.

See Sections 5.7.1 and 6.1 for additional guidance.

### 5.6.3 Laboratory Assessments

Below is a table of the safety laboratory tests that will be performed locally during the conduct of the study. See Table 1 for study visit collection dates.

Chemistry		Coagulation	Urine	Hematology
Sodium	BUN	PT/aPTT	uPCR	CBC including
Potassium	Creatinine			platelet number and
Chloride	Uric Acid			differential
Bicarbonate	Total bilirubin	Thyroid Function		
Total protein	Direct bilirubin	TSH		
Albumin	Alkaline phosphatase	Free T4		
Calcium	LDH			
Magnesium	AST (SGOT)			
Phosphorus	ALT (SGPT)			
Glucose	CRP			

#### 5.6.3.1 Pharmacokinetic and ADA samples

Subjects randomized to AGS-16C3F, will have blood samples drawn for PK and ADA formation assessments. Refer to Table 1 and Table 2

### 5.6.4 Electrocardiogram (ECG)

ECGs will be done in triplicate for all timepoints, approximately 3-5 minutes between each assessment. Ensure that the subject is in the same position for every reading.

ECGs will be collected at Screening, C1D1, and at the Safety Follow-Up visits.

For subjects randomized to AGS-16C3F, on C1D1, the ECGs will be taken predose (anytime predose on actual dosing day) and again 2 hours after the end of infusion, when the total prescribed dose has been administered (e.g., 2 h after the end of infusion).

For subjects randomized to axitinib, on C1D1, the ECGs will be taken predose (anytime predose on actual dosing day) only.

### **5.6.5 Ocular Assessments**

A complete eye exam will be done during screening. Subjects randomized to AGS-16C3F, will have a complete eye exam done after the Cycle 2 Day 1 dose but before the Cycle 3 Day 1 dose, after the Cycle 5 Day 1 dose but before the Cycle 6 Day 1 dose, and as clinically indicated. Subjects randomized to axitinib, will have a complete eye exam done post baseline as clinically indicated. The frequency of ophthalmology follow-ups outside of protocol requirement is at the discretion of the Investigator and ophthalmologist.

The ophthalmologist will complete a study provided cover form, capturing all pertinent information, and submit it along with the ophthalmology report to the investigator. Please see the Study Guide for the form and for complete instructions.

At the screening (baseline) ophthalmology visit, the complete eye exam will consist of Visual Acuity with Snellen Chart, best corrected visual acuity (BCVA), intraocular pressure (IOP), extraocular movement (EOM), pupils, external exam, slit lamp exam, and dilated fundoscopic exam.

For post baseline ophthalmology visits, the complete eye exam will be the same as the baseline visit, but the dilated fundoscopic exam may be deferred if not clinically indicated (i.e., if there is no change in vision or if the vision change can be explained as a non-retinal event). If deferred, an undilated fundoscopic exam is still required as part of the full eye exam.

The Schirmer's test (with and without anesthetic) is optional if subject has dry eyes at screening (baseline).

#### **5.6.5.1 Symptom Based Ocular AEs**

Ocular symptoms reported by the subject during clinic visits will be graded per CTCAE v4.03 (i.e., symptom based assessment) and this will guide the treatment decision for that visit and the necessity for a follow up ophthalmology consult.

An Eye Symptom Questionnaire (ESQ) will be administered at every visit in the oncology clinic. Please see the Study Guide for the form and for complete instructions. During screening, the ESQ will be completed for both Cancer Treatment History and Screening sections.

The ocular symptom AEs must be collected in the eDC system.

If a subject reports ocular symptoms, the following guidelines may be used:

**Table 10 Subject Reported Symptom Based Ocular AE (i.e., per CTCAE v4.03)**

Grade	Study Treatment Action	Ophthalmology Referral
1	Continue per dose and schedule (i.e., AGS-16C3F 1.8 mg/kg q3w or axitinib 5 mg, twice daily)	May be done at Investigator discretion
2	May continue treatment per dose and schedule at Investigator discretion	Required; must occur prior to the subsequent cycle.
3	Hold treatment	Required; must occur prior to the subsequent cycle.

### 5.6.5.2 Clinical Ocular Adverse Events (AE)

Clinical Ocular AEs are objective findings (e.g., keratitis, macular edema, retinal degeneration) from the ophthalmology evaluation.

Clinical Ocular AE grading will be determined based on visual acuity (VA) change from screening (baseline).

This will be done as follows:

- Step 1. Determine baseline VA for each eye. Subject should have the VA measured with or without glasses depending on the subject's requirement for daily use for distance vision. Use [Table 12](#) and identify the row of the baseline vision for each eye.
- Step 2. Subsequent eye exam VA (obtained under same conditions as screening [baseline]), determine if a change in vision is present. If so, use the row in [Table 12](#) identified in Step 1, to locate the current VA and determine the number of line-of-vision-change from baseline for each eye; this is expressed as the number in parenthesis. Also note the grade of the VA for each eye.
- Step 3. Between the two eyes, determine the eye with greater line-of-vision-change from baseline (delta). The Clinical Ocular AE grade for the subject is the grade of the worse (delta) eye. See examples 1 and 2 in [Table 11](#). In the event both eyes have the same delta, then the Clinical Ocular AE grade comes from the eye with the worse new vision. See example 3 in [Table 11](#).

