### **3.3 Exclusion Criteria**

1. Has previously been treated with axitinib, AGS-16C3F, or AGS-16M8F
2. Has untreated brain metastasis. In the case of a solitary brain metastasis which has been resected, there must be evidence of a disease-free interval of at least 3 months post-surgery. For brain metastases treated with whole brain or stereotactic radiation therapy, brain imaging must be stable  $>$  3 months. All subjects previously treated for brain metastases must be stable off corticosteroid therapy for at least 28 days prior to C1D1.
3. Has uncontrolled hypertension defined as blood pressure  $>$  150/90 on medication(s) by 2 blood pressure readings taken at least 1 hour apart.

4. Has gastrointestinal abnormalities including:
  - a. inability to take oral medication;
  - b. requirement for intravenous alimentation;
  - c. prior surgical procedures affecting absorption including total gastric resection;
  - d. active gastrointestinal bleeding, unrelated to cancer, as evidenced by hematemesis, hematochezia or melena in the past 3 months without evidence of resolution documented by endoscopy or colonoscopy;
  - e. malabsorption syndromes such as celiac disease, cystic fibrosis, inflammatory bowel disease, systemic sclerosis, and carcinoid syndrome
5. Has ocular conditions such as:
  - a. Active infection or corneal ulcer
  - b. Monocularity
  - c. Visual acuity of 20/70 or worse in both eyes
  - d. History of corneal transplantation
  - e. Contact lens dependent (if using contact lens, must be able to switch to glasses during the entire study duration)
  - f. Uncontrolled glaucoma (topical medications allowed)
  - g. Uncontrolled or active ocular problems (e.g., retinopathy, macular edema, active uveitis, wet macular degeneration) requiring surgery, laser treatment, or intravitreal injections
  - h. Papilledema or other active optic nerve disorder
6. Has used any investigational drug (including marketed drugs not approved for this indication)  $\leq$  14 days of C1D1. No time limit applies to the use of marketed drugs approved for this indication provided that the subject has progressed on the treatment and all toxicities attributable to the drug have resolved, returned to baseline or stabilized.
7. Has known sensitivity to any of the ingredients of:
  - a. investigational product AGS-16C3F (Refer to [IB](#) for list of ingredients) and/or,
  - b. Inlyta® (axitinib) (Refer to product package insert) and/or,

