**5.6.5.2.1 Treatment Guidelines for Clinical Ocular Toxicities**

Corneal Clinical Ocular AEs

- If Clinical Ocular AE is Grade 3, Medical Monitor will be consulted for treatment decision.
- If Clinical Ocular AE is Grade 4, subject will be permanently discontinued from study treatment.

Non-corneal Related Clinical Ocular AEs

- Clinical Ocular AEs other than ocular surface disease/keratopathy in nature, **irrespective of the grade, must be discussed with the Medical Monitor before the subsequent dose (per axitinib product label, patients treated with this product experienced both retinal artery and retinal vein occlusions. Please see product label for details).**
- If the subject develops a need or is recommended to have cataract surgery while on treatment in the study, discuss each case with the Medical Monitor.

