**Table 12 Visual Acuity Grading Chart**

Baseline vision (with or without correction, based on patient's daily functional distance vision)	Grade 1* (no change in vision from baseline)	Grade 2 (delta vision change = Number of line change in vision from baseline)	Grade 3 (delta vision change = Number of line change in vision from baseline)	Grade 4 (delta vision change = Number of line change in vision from baseline)
20/20	20/20	20/25 (1) 20/30 (2) 20/40 (3)	20/50 (4) 20/60 (5) 20/70 (6) 20/80 (7) 20/100 (8) 20/125 (9)	20/200 (10) or worse
20/25	20/25	20/30 (1) 20/40 (2) 20/50 (3)	20/60 (4) 20/70 (5) 20/80 (6) 20/100 (7) 20/125 (8)	20/200 (9) or worse
20/30	20/30	20/40 (1) 20/50 (2) 20/60 (3)	20/70 (4) 20/80 (5) 20/100 (6) 20/125 (7)	20/200 (8) or worse
20/40	20/40	20/50 (1) 20/60 (2) 20/70 (3)	20/80 (4) 20/100 (5) 20/125 (6)	20/200 (7) or worse
20/50	20/50	20/60 (1) 20/70 (2) 20/80 (3)	20/100 (4) 20/125 (5)	20/200 (6) or worse
20/60	20/60	20/70 (1) 20/80 (2) 20/100 (3)	20/125 (4)	20/200 (5) or worse
20/70	20/70	20/80 (1) 20/100 (2) 20/125 (3)	N/A	20/200 (4) or worse
20/80	20/80	20/100 (1) 20/125 (2)	N/A	20/200 (3) or worse
20/100	20/100	20/125 (1)	N/A	20/200 (2) or worse
20/125	20/125	N/A	N/A	20/200 (1) or worse
20/200	20/200	N/A	N/A	Worse than 20/200

\*Grade 1 is the same as screening (baseline) from a VA perspective. The Grade 1 Clinical Ocular AE will be an event when the AE is present (e.g., keratopathy) but there is no change in VA from baseline and the subject has little to no symptoms. If the AE is not treated aside from using artificial tears, then it would be considered Grade 1.

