- Subsequent eye exam VA (obtained under same conditions as screening (baseline)), determine if a change in vision is present. If so, use the row in Table L identified in Step 1, to locate the current VA and determine the number of line-of-vision-change from baseline for each eye; this is expressed as the number in parenthesis. Also note the grade of the VA for each eye.
- Between the two eyes, determine the eye with greater line-of-vision-change from baseline (delta). The Clinical Ocular AE grade for the subject is the grade of the worse (delta) eye. See Examples 1 and 2 in Table M.
- In the event both eyes have the same delta, then the Clinical Ocular AE grade comes from the eye with the worse new vision. See Example 3 in Table O.

Table O. Examples of Clinical Ocular AE: Keratopathy

	Baseline (CC)	New VA (CC)	Lines VA Change	VA Grade	Clinical Ocular AE Grade
Example 1					
OD	20/20	20/50	(4)	3	Grade 3
OS	20/40	20/70	(3)	2	
Example 2					
OD	20/60	20/125	(4)	3	Grade 3
OS	20/100	20/200	(2)	4	
Example 3					
OD	20/30	20/100	(5)	3	Grade 4
OS	20/60	20/200	(5)	4	

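### The subject-level ocular grade follows the eye that lost more lines, not the eye with the higher grade, so it can fall from Grade 4 to Grade 3 or 2 when the second eye also worsens

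*Protocol*

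**What the plan says.** Protocol 5.6.5.2 grades clinical ocular events by change in visual acuity from baseline. Each eye receives a line change and a grade from Table 12. Step 3 then reduces the two eyes to one subject grade: "The Clinical Ocular AE grade for the subject is the grade of the worse (delta) eye". The worse eye here is the one with more lines lost. On a tie the eye with the poorer new acuity decides. The SAP repeats both parts of the rule in 19.7.1.1, including "In the event both eyes have the same delta, then the Clinical Ocular AE grade comes from the eye with the worse new vision".

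In Table 12, Grade 4 is reached at 20/200 from every baseline between 20/20 and 20/125. The number of lines this takes depends on the starting point: the 20/70 row shows "20/200 (4) or worse" and the 20/125 row shows "20/200 (1) or worse".

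For corneal events, 5.6.5.2.1 says: "If Clinical Ocular AE is Grade 4, subject will be permanently discontinued from study treatment". At Grade 3 the Medical Monitor is consulted. No corneal action is listed for Grade 2.

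At entry, exclusion 5c bars "Visual acuity of 20/70 or worse in both eyes", so one eye at 20/70 to 20/125 is allowed if the other is better than 20/70. Exclusion 5b bars "Monocularity" but gives no acuity threshold for it.

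**The concern.** The grade is set by where an eye ends up, while the choice of eye is set by how far it moved. An eye that starts poor can reach Grade 4 in a few lines and then be outvoted by a better eye that lost more lines but sits at Grade 2 or 3. A subject whose second eye also deteriorates can therefore receive a lower grade than one whose second eye stayed stable.

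This matters because Protocol 1.4 names ocular toxicity as the compound's main distinctive toxicity. The subject grade feeds the safety tables and determines which corneal action applies.

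**Working it through.** **Inputs.** Acuity levels, line counts and grades come from Protocol Table 12; the selection rule from Step 3; eligibility from exclusion 5c. SAP Table N prints no line counts in its Grade 4 column, so the Protocol's counts are used for Grade 4 eyes. A Grade 4 eye is taken as exactly 20/200, because worse acuity is not numbered. Eyes already at 20/200 at baseline are left out for the same reason.

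**The plan's own examples (Protocol Table 11).**
- Example 1: 4 lines (Grade 3) against 3 lines (Grade 2) gives Grade 3, as printed.
- Example 2: 20/60 to 20/125 is 4 lines (Grade 3) and 20/100 to 20/200 is 2 lines (Grade 4). Since 4 > 2, the subject is Grade 3, as printed, with a Grade 4 eye present. Had the first eye stayed at 20/60, then 2 > 0 and the subject would be Grade 4.
- Example 3: 5 lines each, tie, worse new acuity 20/200, Grade 4, as printed.

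**Smallest trigger for a fall to Grade 2.** 20/125 to 20/200 is 1 line, Grade 4. With the other eye unchanged at 20/20 (0 lines) the subject is Grade 4. With the other eye at 20/30 (2 lines, Grade 2), 2 > 1 and the subject is Grade 2.

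**All combinations.** One eye falls to 20/200 and the other takes every equal-or-worse value, for all baseline pairs that 5c allows. Right and left are not yet distinguished:

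| Baseline of the Grade 4 eye | Lines to 20/200 | Subject graded 3 | Subject graded 2 |
|---|---|---|---|
| 20/20, 20/25 | 10, 9 | 0 | 0 |
| 20/30 | 8 | 1 | 0 |
| 20/40 | 7 | 3 | 0 |
| 20/50 | 6 | 6 | 0 |
| 20/60 | 5 | 10 | 0 |
| 20/70 | 4 | 15 | 0 |
| 20/80 | 3 | 21 | 0 |
| 20/100 | 2 | 21 | 6 |
| 20/125 | 1 | 21 | 12 |

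- Total below Grade 4: 98 + 18 = 116, or 232 counting right and left separately. Graded 2: 18, or 36.
- Denominator: the six baselines better than 20/70 have 11+10+9+8+7+6 = 51 possible outcomes, and the four from 20/70 to 20/125 have 5+4+3+2 = 14. With the Grade 4 eye fixed: 6 × (51+14) + 4 × 51 = 594. There are 100 − 16 = 84 eligible ordered baseline pairs, each with one outcome where both eyes are at 20/200. So 2 × 594 − 84 = 1104, and 232/1104 = 21%.
- One eye starting at 20/70 to 20/125: denominator 2 × (204 + 84 − 24) = 528, numerator 2 × (15+21+27+33) = 192, which is 36%.
- Both eyes better than 20/70 at baseline: 232 − 192 = 40, i.e. 2 × (1+3+6+10), all falls to Grade 3. For example, 20/60 to 20/200 is 5 lines (Grade 4) and 20/20 to 20/70 is 6 lines (Grade 3), so the subject is Grade 3.

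**SAP Table O, Example 3.** It labels 20/30 to 20/100 as 5 lines. Table N counts 20/40 (1), 20/50 (2), 20/60 (3), 20/70 (4), 20/80 (5), 20/100 (6). The other eye, 20/60 to 20/200, is 5 lines. With 6 > 5 there is no tie and the rule returns Grade 3, not the printed Grade 4. The Protocol's version uses 20/80, which is 5 lines and consistent.

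**The case against.** The strongest reply is that this is a disclosed choice. Step 3, Table 12 and Example 2 agree with one another, and Example 2 prints the very outcome at issue. That stands: the Protocol does not contradict itself on the rule. But Example 2 shows only that the rule was written this way. Nothing explains why loss in a second eye should lower the grade.

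Other limits also stand:
- SAP 19.7.1 already summarises acuity change and grade for each eye separately, and lists the full eye data by subject. A Grade 4 eye is therefore not lost from the report, only from the subject-level grade.
- The fall needs both eyes to have worsened at the same exam. If the Grade 4 eye is found earlier with the other eye stable, Grade 4 is assigned then, any corneal action follows, and the worst post-baseline summary keeps it.
- Other safeguards do not depend on Step 3: symptom-based rules (Table 10), Medical Monitor discussion of non-corneal events at any grade, investigator review of each ophthalmology report, and discontinuation for an unacceptable event (6.1). Ocular events entered as AEs also appear in the general AE tables.
- The analyses use the investigator's assigned grade, so the Table O slip is editorial and alters no result by itself.
- Protocol version 6.0 is dated 12 August 2020 and the planned period ends in 3Q2020, so a protocol change could reach few subjects, if any. The SAP changes remain useful.

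A reader might infer that Grade 4 ocular toxicity on AGS-16C3F will be under-reported, mainly in subjects with unequal vision. The documents do not support this. They give no distribution of baseline acuity or of line loss, and Protocol 1.4 reports no Grade 4 ocular toxicity among 13 Phase 1 subjects at 1.8 mg/kg, although that sample is small.

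**Conclusion.** The subject-level Clinical Ocular AE grade is not monotonic in visual loss. With both eyes worse at one exam, a subject with a Grade 4 eye can be graded 3. The subject can be graded 2 if the Grade 4 eye started at 20/100 or 20/125; from 20/70 or 20/80 the fall stops at Grade 3. The subject grade, and the corneal actions in 5.6.5.2.1 that depend on it, can then understate the worse-graded eye.

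It would be tempting to blame exclusion 5c. The 40 combinations with both eyes better than 20/70 show that the source is Step 3 combined with Table 12. Exclusion 5c only widens the effect, and all 36 falls to Grade 2 need a poor eye that it admits.

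The 21% and 36% describe unweighted table combinations, in which a 10-line loss counts the same as a 1-line loss. They are not proportions of subjects, and no such proportion can be derived. Separately, SAP Table O Example 3 contradicts SAP Table N.

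**What to change.** 1. The sponsor should reconcile Step 3, Table 12, Table 11 Example 2 and 5.6.5.2.1, and state whether a subject's grade is meant to fall when the second eye also worsens. Which clinical rule should apply is for the sponsor to settle.
2. In SAP 19.7.1, alongside the Step 3 grade and the existing by-eye summaries, tabulate by arm the higher of each subject's two eye grades at planned timepoints, worst post-baseline and final assessment.
3. Correct SAP Table O Example 3 so that it agrees with Table N and with Protocol Table 11 (20/30 to 20/80, 5 lines).

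The cost is a clarifying statement, one extra table from per-eye data already collected, and one edited cell. The reported count of Grade 4 subjects may rise in the new table.
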